Appendix A

This report provides information on detailed technical methods for handling of issues for the analysis of 6-month client data as well as 12-month and 3 years follow-ups.

Table of Contents		Page
A1	Analytic Sample	A-2
A2	Weighting	A-3
A3	Multiple Imputation	A-4
A4	Analyses	A-6
A5	References for Appendix	A-10

A1. Analytic Sample

Enrollment

The study settings were South Los Angeles and Hollywood-Metro. Participant sampling (program and client recruitment) and randomization are described in greater detail in prior publications. Within enrolled programs, clients were screened for eligibility in waiting rooms (consecutive selection) or events (random selection) between March 2010 to November 2010 by community members blinded to intervention condition and supervised by RAND. Staff approached 4,645 adults (age \geq 18) over 2-3 days per program; 4440 (96%) agreed to screening. Study eligibility was limited to clients providing contact information and depressed based on a score of 10 or greater on a modified 8-item Patient Health Questionnaire (PHQ-8) (3). Of 4,440 screened, 1,322 (30%) were eligible and 1246 (94%) consented. In our previous publications,(1-3) we created enrollment weights based on propensity weighting adjustment, by fitting logistic regression models to predict the enrollment among those eligible. The reciprocal of the predicted response probability was used as the enrollment weight for each participant. See Supplementary Materials in publications. ¹⁻⁵

Telephone survey

Baseline survey. Between April 27, 2010-January 2, 2011, we approached 1,246 consented clients for baseline telephone survey conducted by survey staff blinded to intervention condition and 981 clients (79% of 1246 consented, RS: 492, CEP: 489) completed the baseline, 36 refused (RS: 17, CEP: 19), 227 were unable to contact (RS: 96, CEP: 131), and 2 deceased (RS: 1, CEP: 1).

6 month follow-up survey. Between November 2, 2010 and August 11, 2011, we approached 1093 participants (RS: 540, CEP: 553) for 6-month follow-up telephone survey; 153 enrolled participants were excluded from the contact list because their baseline survey response status was in one of following categories: final refusal, ill or incarceration, unable to contact, or deceased. Of 1093 attempted for 6-month follow-up, N=759 (69% of attempted, RS: 380, CEP: 359) completed the survey, 12 refused (RS: 3, CEP: 9), 321 were unable to contact (RS: 157, CEP: 164), and 3 deceased (RS: 1, CEP: 2).

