Enrollment The enrollment weight was intended to make the enrolled sample (n=1,246) representative of a specific target population.^{6,7} That target population was defined as people who were: age 18 or older, visited a participating CPIC sites during our screening window, screened positive for PHQ-8, and provided contact information. We created enrollment weights based on propensity weighting adjustment, by fitting logistic regression models to predict the enrollment among those eligible. The reciprocal of the predicted response probability was used as the enrollment weight for each participant. Five versions of the enrollment weight were created corresponding to five imputed screener data, because imputed predictors from the

screeener data were used in fitting logistic regressions. Common predictors of age, community, and type of programs were used in all models.

Attrition The analytic sample for 6 months is comprised of 1,018 participants who completed baseline, or 6-month telephone follow-up surveys. We used nonresponse weighting to address missing data for subjects who did not who did neither complete baseline nor 6 months follow-up telephone surveys. We started with a large set of independent categorical variables to be considered for a logistic regression on the outcome of response among enrolled participants. The final model included predictors that were significant ($p < 0.05$) for either intervention arm (age, gender, ethnicity, living situation, income, US born), as well as for two design variables (community and sector of the screening program). The final weights defined on the analytic sample were the product of the two adjustment factors for enrollment and nonresponse. See Supplementary Materials in publications. We applied the weights to the 36-month outcome analysis excluding 24 deceased cases (1,004 attempted - 24 deceased = 980). The weights for 3-year main analysis defined on the analytic sample were the product of the two adjustment factors for enrollment and nonresponse. See Supplementary Materials in previous publications.¹⁻³

For 4-year follow-up, we tested bivariate associations between an indicator for responding at the 4-year survey and demographic and clinical characteristics at baseline and 3 years.⁵ The weighting model to predict follow-up status from 3-year sample included screener sector, age, education, working for pay, PCS-12, poor mental health-related quality of life at baseline, and risk for homelessness at 3 years.

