A3. Multiple Imputation

Item-level Missing Data We used an extended hot deck multiple imputation technique to impute missing values for item-level nonresponse.^{8,9} The procedure was based on cycling through each missing-data pattern on each variable with incomplete items. This method involved two steps: 1) forming imputation classes based on the predicted mean of the variable being imputed from a multiple regression model, and 2) drawing imputations at random from observed data within each class based on an approximate Bayesian bootstrap. To reflect the uncertainty of donor cells we created bootstrap weights and then used the product of the bootstrap weights in the multiple imputation model. Five imputed datasets were created. Each of the imputed data sets differs by the bootstrap weight and the seed used to obtain the random number employed in the hot deck

imputation. Data on several hundred, multi-item scales were collected at screener, baseline and follow-up time points. Most variables had item-level missingness rates of less than 5% except for baseline income and MINI variables. With imputations stratified by intervention arms, 5 alternative imputed datasets were produced for screener, baseline, 6 month, 12 month, and 3 year follow-ups, and multiple imputation inferences were used in all analysis.^{10, 11}

The approach for selecting variables for multiple regression models was intended to preserve the associations and relationships among variables. In general, we identified common predictors for all imputation models including design variables (community, type of programs), social demographic variables (age, gender, ethnicity, marital status, education, living situation, income, and working status), and PHQ-8 score. For baseline, 6 months, 12 months, and three year data, baseline health variables (count of chronic medical conditions, PCS12 and MCS12) were included. In addition to these common predictors, each imputation model also included other predictors to be used in later analyses of interest. The order in which variables were imputed was determined based on a judgment of the analytic importance of the variables and the degree of missing data. Earlier imputed values were used during subsequent imputation steps, implying some dependence on the order in which variables were imputed.

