Unit-Level Multiple Imputation We used a hot deck multiple imputation procedure based on an approximate Bayesian bootstrap method for unit-level missing data.^{12, 13} This model assumes that both missingness and dropout arise from mechanisms that are missing at random (MAR) in the sense defined by Rubin. Our imputation techniques attempted to include information related to the missing values whenever possible. We first modeled the propensity of response at a given time point (coded 1 if response and 0 if nonresponse). In Step 2, we stratified cases based on the quintiles of the propensity scores and used the approximate Bayesian bootstrap to select donors. In practice these procedures were applied in sequence for the baseline, 6-month, 12-month, and 3-year data, with imputations stratified by two intervention arms. We started with imputing baseline. For each of the 5 item-level imputed screener datasets, we imputed a unit-level imputation baseline dataset. Limited to the analytic sample of 1,018, we then used baseline variables as predictors for modeling 6 and 12-month follow-up data and produced unit-level imputation datasets. In modeling the logistic regression of predicting response propensities, we started with a large set of independent variables. The final baseline model included the predictors: age, gender, ethnicity, income, living situation, US born, community, and type of

screening program. The 6-month models included participants characteristics assessed at screener (age, gender, ethnicity, health insurance, and type of screening program.), and baseline clinic and service variables (multiple chronic conditions, alcohol abuse or use of illicit drugs, any depression care). The 12-month models included additional variables: community, PHQ-8 assessed at screener, mental wellness, homeless status at baseline. The 3 years models included age, gender, ethnicity, employment status, ≥ 3 chronic conditions, homeless, 12-month alcohol abuse or use of illicit drugs, no place to stay for at least two nights in the past 6 months, type of screening program, and community with additional stratum variable sector (social-community screening sector vs healthcare Screening Sector) in Step 2. Values for participants who were deceased were not imputed.

A4. Analyses

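### The same five imputed datasets carry whole-wave nonresponse of about 25% at 6 months and 39% at 3 years, so some precision is lost and borderline p-values depend on the random seed

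*Combined protocol and SAP*

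**What the plan says.** Appendix A3, under item-level missing data, states "Five imputed datasets were created" and then that "5 alternative imputed datasets were produced for screener, baseline, 6 month, 12 month, and 3 year follow-ups". The same paragraph reports that "Most variables had item-level missingness rates of less than 5" per cent, with baseline income and the MINI variables as exceptions, and that multiple-imputation inference was used throughout.

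The unit-level part of A3 handles participants who missed a whole survey. It starts from the same five: "For each of the 5 item-level imputed screener datasets, we imputed a unit-level imputation baseline dataset". It then moves to the follow-ups: "Limited to the analytic sample of 1,018, we then used baseline variables as predictors for modeling 6 and 12-month follow-up data". The weights in A2 follow the same count: "Five versions of the enrollment weight were created corresponding to five imputed screener data".

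A2 defines the samples: "The analytic sample for 6 months is comprised of 1,018 participants who completed baseline, or 6-month telephone follow-up surveys". At 3 years it analyses 980 (1,004 attempted less 24 deaths). A1 gives the completers: "N=759 (69% of attempted, RS: 380, CEP: 359) completed the survey" at 6 months, 733 at 12 months and 600 at 3 years. A4 describes the 6-month and 3-year analyses as weighted endpoint analyses. It describes the main 12-month analysis as an unweighted repeated-measures model on available data.

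No reason for five is given. No FMI, Monte Carlo error or rerun with more imputations is reported.

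**The concern.** The number of imputations needed grows with the share of information that is imputed. Five suits a few per cent of missing items. Here it also serves a step that fills in a quarter to two fifths of the endpoint outcomes. Two things follow. The between-imputation variance is estimated on four degrees of freedom, which lowers the reference degrees of freedom and widens intervals. The pooled estimate and its standard error also carry random error from the imputation draws, so the same data and code with another seed can give a noticeably different p-value. At stake is whether a borderline primary result at 6 months or 3 years reflects the data or the draw.

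**Working it through.** **Stated figures reproduced.** 759/1,093 = 69.4% (stated 69%); 733/974 = 75.3% (stated 75%); 1,004 − 24 = 980.

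**Whole-wave share missing from each analytic sample.**
- 6 months: (1,018 − 759)/1,018 = 259/1,018 = 25.4%. The arm counts add to 380 + 359 = 739; with 739 completers the share is 279/1,018 = 27.4%.
- 12 months: (1,018 − 733)/1,018 = 285/1,018 = 28.0%.
- 3 years: (980 − 600)/980 = 380/980 = 38.8%. A1 also gives 1,014 attempted; that would make it 390/990 = 39.4%.

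The few deaths, which are not imputed, barely change the 6- and 12-month shares.

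**Assumptions.** FMI (γ) is not in the documents. I take 0.10 (strong predictors), 0.25 and 0.39 (equal to the missing share at 6 months and 3 years). Complete-data degrees of freedom ν_c = 87: the 89 programs named in the 3-year extension section, less 2, which is the plan's own rule in its power section.

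**Formulas.** Scale the total variance at unlimited m to 1, so within-variance is 1 − γ and between-variance is γ.
- T = 1 + γ/m; λ = (1 + 1/m)γ/T
- Barnard-Rubin: 1/ν = λ²/(m − 1) + 1/ν_obs, with ν_obs = [(ν_c + 1)/(ν_c + 3)] ν_c (1 − λ)
- half-width = t(0.975, ν) × √T

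**Worked case, γ = 0.25.**
- m = 5: T = 1.05, λ = 0.286, ν = 27.1, t = 2.051, half-width 2.102.
- m = 50: T = 1.005, λ = 0.254, ν = 58.6, t = 2.001, half-width 2.006.
- Ratio 2.102/2.006 = 1.048.

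At γ = 0.39 the half-widths are 2.217 (ν = 14.7) and 2.023 (ν = 44.2), ratio 1.096. At γ = 0.10 they are 2.020 and 1.994, ratio 1.013.

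**Power.** Noncentral t, with the effect set so that m = 50 gives 80%.

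**Seed dependence.** Simulated over seeds (400,000 per case): the pooled estimate varies with variance γ/m, and the estimated between-variance as γ × χ²(m − 1)/(m − 1). The reference p is the value that the same data would give with unlimited imputations.

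| FMI | Interval wider, m = 5 v 50 | Power at m = 5 | Reference p 0.03: seeds with p < 0.05, m = 5 / 50 | Reference p 0.01: seeds with p < 0.025, m = 5 / 50 |
|---|---|---|---|---|
| 0.10 | 1.3% | 79.0% | 87% / >99% | 95% / >99% |
| 0.25 | 4.8% | 76.6% | 67% / 99% | 75% / >99% |
| 0.39 | 9.6% | 73.4% | 57% / 95% | 62% / 99% |

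The last column is the 6-month case, where A4 applies Bonferroni to two primary outcomes (0.05/2 = 0.025).

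For a reference p of 0.05, the middle 90% of seeds at m = 5 runs from 0.018 to 0.151 (γ = 0.25) and from 0.012 to 0.203 (γ = 0.39). At m = 50 it runs from 0.036 to 0.069 and from 0.032 to 0.078.

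**The case against.** The strongest reply is that this is a matter of efficiency, not an error. That stands. A reader might infer that five imputations bias the treatment effect or invalidate the intervals. The documents do not support that: Rubin's rules charge for small m through the variance and the t reference, and relative efficiency, 1/(1 + γ/5), is still 0.95 at γ = 0.25 and 0.93 at γ = 0.39. Clear-cut results would not change.

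A second reply is that good predictors bring FMI below the missing share. This also stands as a caution, which is why 0.10 is in the range. The documents do not make a low value secure, though. The unit-level step draws donors within quintiles of response propensity, by arm. The predictors listed for the 6-month and 3-year propensity models include neither MCS-12 nor PHQ-8; those scores appear in the item-level models.

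Third, a reader might infer that a primary result would simply cross 0.05. The stated rules differ: Bonferroni at 6 months, and at 3 years FDR-adjusted p-values for the primary pair, read alongside the standard ones. Seed dependence persists at the Bonferroni level, as the table shows; I have not simulated the FDR procedure.

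Fourth, it is tempting to count 12 months equally. The main 12-month model is described as using available data, although A3 says multiple imputation was used in all analyses. The role of imputed outcomes there is unclear, so I do not rely on it.

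Finally, raw-data results accompany the models, and nonignorable-missingness checks are described for the 12-month analysis. Both are useful, but neither measures Monte Carlo error.

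**Conclusion.** The point holds as a cheap improvement to the 6-month and 3-year endpoint analyses. With FMI between 0.10 and 0.39 and about 87 complete-data degrees of freedom, five imputations cost about 1% to 10% in interval width and up to about 7 points of power against fifty. The seed dependence matters more: if FMI is near the missing share, a reference p of 0.03 would miss 0.05 in about a third of seeds at 6 months and over two fifths at 3 years. If FMI is only 0.10, it would miss in about one seed in eight. These sizes rest on the assumed FMI, which the documents do not report. The missing shares follow directly from the stated counts, subject to the 759/739 and 1,004/1,014 discrepancies, which do not change the conclusion.

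**What to change.** Rerun the item-level and unit-level hot deck, with the matching enrolment weights, using at least 40 to 50 imputations. Report the FMI and the Monte Carlo error of the estimate and p-value for each primary outcome at 6 months and 3 years. State in A4 whether the main 12-month analysis uses imputed outcomes, and reconcile the 6-month completer count.

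No new data or design change is needed. The cost is computing time for a sequential imputation over several hundred scales, and refitting of the weights for each dataset. Seed dependence is much reduced but not removed: at FMI 0.39, a reference p of 0.03 still misses 0.05 in about 5% of seeds with fifty imputations. The reported Monte Carlo error would show whether more are needed.

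### Unit-level imputation at 6 months and 3 years picks donors without any listed MCS-12 or PHQ score, which costs some precision, chiefly for poor MCS-12

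*Combined protocol and SAP*

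**What the plan says.** Appendix A3 (Unit-Level Multiple Imputation) first models the probability of responding at a wave. Then, separately by arm, "we stratified cases based on the quintiles of the propensity scores and used the approximate Bayesian bootstrap to select donors". At 3 years, sector is an added stratum.

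- For 6 months the list reads "The 6-month models included participants characteristics assessed at screener (age, gender, ethnicity, health insurance, and type of screening program"), together with "baseline clinic and service variables (multiple chronic conditions, alcohol abuse or use of illicit drugs, any depression care").
- For 3 years it opens "The 3 years models included age, gender, ethnicity, employment status" and goes on to chronic conditions, homelessness, alcohol or drug use, lack of a place to stay, program type and community.

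Neither list names a PHQ or MCS-12 score. The 12-month list does add screener PHQ-8 and mental wellness, so this point does not extend to it. The lists are the final ones; for the response models, "we started with a large set of independent variables".

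The item-level part of A3 works differently. Its classes come from the predicted mean of the variable being imputed. PHQ-8 is a common predictor, for the survey waves "baseline health variables (count of chronic medical conditions, PCS12 and MCS12) were included", and "each imputation model also included other predictors to be used in later analyses of interest".

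Appendix A4 adjusts the 6-month and 3-year endpoint models for the baseline value of the outcome. The 6-month text, whose strategy the 3-year analysis follows, judges significance from the regression coefficient and adds unadjusted raw results as a robustness check.

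**The concern.** An imputation procedure should carry the variables on which the analysis model conditions. Here a missing outcome is borrowed from someone with a similar chance of responding, whatever either person's earlier score was. The filled-in outcome is then only weakly tied to the client's own baseline. The baseline coefficient fades, the conditional log odds ratio for intervention drifts toward its marginal value, and information in the earlier scores is lost. Power on the coefficient that the plan tests is at stake.

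**Working it through.** **1. The plan's own power figure.** Table 4 gives a detectable effect of 0.20-0.22 SD for 780 analyzed. With 390 per arm and d = 0.20, power is 0.798, and at ICC 0 the detectable effect is 0.201. At ICC 0.02 with 80 programs, m = 780/80 = 9.75 and VIF = 1 + 8.75 × 0.02 = 1.175, giving 0.220; with 100 programs it is 0.216. The plan's figure is reproduced.

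**2. Imputed shares** (Appendix A1, A2).
- 6 months: 1,018 − 759 = 259; 259/1,018 = 25.4%. It is 256 if the 3 deaths are left out. The printed arm counts, 380 + 359, add to 739; if those are right, the share is 27.4%.
- 3 years: 1,004 − 24 = 980; 980 − 600 = 380; 380/980 = 38.8%. It is 39.4% if 1,014, which A1 also prints, were attempted.

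**3. Were earlier scores available?** A2 states: "The analytic sample for 6 months is comprised of 1,018 participants who completed baseline, or 6-month telephone follow-up surveys". Anyone in that sample without a 6-month survey therefore has a baseline survey. By count, 981 + 759 − 1,018 = 722 have both and 981 − 722 = 259 have baseline only. The 3-year contact list excluded clients with no earlier survey data: 1,246 − 8 deceased − 49 refusals − 185 without data = 1,004. Screener PHQ-8 was part of eligibility.

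**4. Covariates.** Education, family poverty and 12-month depressive disorder are in the A4 models but in neither donor list. Community is also missing at 6 months.

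**5. Mechanism.** If donors are unrelated to baseline, the baseline slope shrinks by the imputed share. At a slope of 0.50, 0.50 × (1 − 0.254) = 0.37 and 0.50 × (1 − 0.388) = 0.31. Simulation of a continuous outcome gave 0.372 and 0.306.

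**6. Poor MCS-12.** The simulation used 2,000 replicates and 509 or 490 clients per arm. The true effect was about 10.7 points, with dropout alike by arm, five imputations and Rubin's rules. The model was logistic on arm and baseline status. Assumptions: baseline split at the median, no clustering or weights, and a donor covariate correlated 0.1-0.4 with the outcome. The comparator forms within-arm quintiles of the mean predicted from baseline score and that covariate. Ranges run over the three donor correlations (0.1, 0.2, 0.4).

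| Missing | Baseline correlation | log-OR, listed donors | log-OR, score-based | Power loss, points |
|---|---|---|---|---|
| 25% | 0.50 | 0.463-0.467 | 0.485-0.490 | 1.8-2.6 |
| 25% | 0.60 | 0.481-0.491 | 0.523-0.526 | 3.8-4.7 |
| 39% | 0.50 | 0.461-0.463 | 0.488-0.497 | 3.0-5.4 |
| 39% | 0.60 | 0.463-0.477 | 0.518-0.524 | 5.6-9.0 |

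For example, at correlation 0.50 and donor correlation 0.2, power is 83.5% against 86.1% (25% missing) and 69.8% against 75.2% (39%). The standardized risk difference differs by at most 0.07 point in all 12 runs. Monte Carlo error for power is 0.8-1.0 point. A run with ICC 0.02 and cluster-robust errors gave 79.6% against 82.4%, and 65.8% against 71.5%.

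**7. A lower 3-year correlation.** The 0.50 (and the PIC value above 0.60) in the power section is for 12 months. At an assumed 0.30 and 39% missing, the log-OR is 0.435 against 0.442 and power 65.0% against 67.0%.

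**8. Depression status.** Entry required PHQ-8 of at least 10, and A4 puts 995 of 1,018 (97.7%) at risk of subsequent clinical remission. With 97.7% positive at baseline and correlation 0.50, the log-OR is 0.431 under both methods (25%) and 0.438 under both (39%). Power is 78.1% against 80.0%, and 68.0% against 69.6%. At correlation 0.60 and 25% missing, it is 0.438 against 0.444 and 80.1% against 85.3%.

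**The case against.** **The scores may have been used.** The item-level text speaks of predictors common to all imputation models. But it sits under the item-level heading, and the unit-level text gives its own final lists. If the common set had carried over, adding screener PHQ-8 at 12 months would be redundant. The omission stands as written, though a clarification could remove it.

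**The scores may have been tried and dropped as predictors of response.** That is possible. It would answer a worry about bias but not the dilution, because response-propensity cells do not match on outcome.

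**The loss is not uniform.** This stands. The log-OR shrinkage belongs to poor MCS-12, not to both primary outcomes, and the larger 3-year losses need a correlation that the documents support only over 12 months. In the runs without clustering, 6-month power for poor MCS-12 stays at 82-85%, above the 80% target.

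**Other checks exist.** Raw results are presented, the 12-month mixed model for continuous MCS-12 uses within-client covariance, and a 3-year longitudinal analysis is planned. None brings a client's own earlier score into the imputation of the two binary primary outcomes at 6 months or 3 years.

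**A stronger reading is tempting: that the comparison is biased or its false-positive rate inflated.** This needs dropout to depend on earlier outcome differently by arm, which the documents do not show. Under a true null, with an assumed dropout log-odds of 0.4 per SD in one arm only, rejection is about 8% (25% missing) and 10% (39%), and unadjusted raw data would be biased by a similar amount. With 0.4 in both arms it is 4-6%; with 0.2 in one arm, 4-7%. A one-arm effect of 0.4 would give z of about 3.9 or 4.3, so screening the scores would very likely have detected it. Completion was also similar by arm: 364 and 369 at 12 months, 293 and 307 at 3 years. Similar completion does not rule out differential dependence, so this remains a conditional caution.

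**Conclusion.** The concern holds as a loss of precision and is an inexpensive improvement to make. It does not show that the trial's comparison is invalid. The poor MCS-12 figures assume a baseline split near the median, and all sizes except the ICC run ignore clustering and weights. The 3-year correlation is an assumption throughout. For depression, the near-absence of log-OR shift rests on taking the 995 of 1,018 as baseline status, which A4 does not state precisely. The losses would be smaller if the listed predictors carry more outcome information than assumed here. Confidence is medium, because the lists may not record everything that was used.

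**What to change.** 1. For the two primary outcomes at 6 months and 3 years, form donor classes within arm from the predicted mean, as A3 already does for items. Use screener PHQ-8, earlier-wave MCS-12 and PHQ scores, and the A4 covariates. Report this at least as a sensitivity analysis. Merely adding baseline score to the response model would do little: in simulation (correlation 0.50) it moved the baseline log-OR from 1.03 to 1.08 (25% missing) and from 0.84 to 0.89 (39%), whereas predicted-mean classes gave 1.40 and 1.39.
2. If the scores were already used at unit level, correct A3 to say so.
3. Secondary: extend the nonignorable checks, described only for 12 months, to 6 and 36 months and apply the shifts to one arm at a time. A4 does not say whether its shifts were common to both arms.

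The cost is reprogramming, re-running completed analyses, one added table and revised wording in A3 and A4. No new data are needed. Estimates may differ slightly from those already reported and would need a note.
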